5.9 Complaint Handling

To ensure the safety and proper monitoring of the subjects and facilitate the improvement of trial process and drug product, the sponsor will collect complaints related to the investigational drug.

Complaints regarding concomitant medications will be directed to the manufacturer according to the prescribing information of the drugs.

The investigator or designee must complete the following procedures for product complaints in accordance with applicable requirements of the study:

- A drug complaint form specific for clinical trials will be used to document product complaints and relevant description completely.
- The completed product complaint form shall be submitted to the sponsor or designee by fax within 24 hours.

If the investigator is asked to return the product for further investigation, the investigator shall return the product along with a copy of the complaint form.

6 Study Evaluations and Relevant Procedures

6.1 Subject Enrollment

6.1.1 Subject enrollment

The investigator will enroll subjects by the following steps:

1. Obtain the ICF signed by the subjects prior to any study-related procedures.

2. Confirm the subjects' eligibility by the principal investigator or trained designee after reviewing the inclusion/exclusion criteria.
3. Prior to enrollment, the trained designee must mail the subjects' medical information including those regarding the inclusion/exclusion to the sponsor's medical manager for review. The subject can only be enrolled after confirmation by the sponsor's medical manager.

Subjects who do not meet the criteria (screen failures) may be re-screened. If re-screening is considered, the investigator must contact the sponsor's medical manager. Each subject can be re-screened once. The subject must sign the ICF again and receive a new identification number when re-screening.

6.1.2 Enrollment error handling

The inclusion/exclusion criteria must be followed strictly. If an ineligible subject is enrolled, the sponsor's medical manager and investigator must discuss whether to allow the subject to continue participating in the study and whether to use the investigational drug. If the subject is appropriate medically to continue with the study judged by the investigator, which is also agreed with by the sponsor's medical manager, then the subject will continue participating in the study and receive the investigational drug; if the subject is appropriate medically to continue with the study judged by the investigator, which is not agreed with by the sponsor's medical manager, then the subject shall not continue participating in the study (regardless of receiving the investigational drug or not). The investigator must not allow the improperly enrolled subject to continue with the study until receive the written approval from the sponsor.

6.2 Study Plan and Schedule

6.2.1 Screening

The following procedures must be completed during the screening (Day -28 to -1) to ensure subject eligibility:

- Signing of the ICF
- Confirming the inclusion/exclusion criteria
- Recording the demographics, medical history, and prior medications
- Recording the vital signs, height and weight.
- Physical examination
- ECOG PS score

- 12-lead ECG
- Count of whole blood cells/blood biochemistry/routine urinalysis (within 7 days prior to the first dose)
- Pregnancy test (within 3 days prior to the first dose)
- Thyroid function
- HIV antibody, hepatitis B panel, HCV antibody (patients testing positive for HCV antibody shall also be tested for HCV RNA)
- EBV DNA copy number in peripheral blood
- AE evaluation
- Concomitant medication
- Bone marrow biopsy
- Tumor imaging evaluation (PET-CT and contrast-enhanced CT)
- Archival or fresh tumor tissue sample

Refer to Table 1 for schedule of visits during screening.

Refer to Sections 6.3 and 6.4 for details regarding tumor evaluation and safety evaluation.

6.2.2 Baseline (prior to Day 1 of Cycle 1)

- Recording the vital signs
- ECOG PS score
- Immunogenicity
- AE evaluation
- Concomitant medication
- Disease-related symptom evaluation
- EQ-5D-5L and EORTC QLQ-C30
- Blood sampling for biomarkers

6.2.3 Treatment period

- Recording the vital signs
- Physical examination
- ECOG PS score
- 12-lead ECG
- Count of whole blood cells/blood biochemistry/routine urinalysis
- Thyroid function

- EBV DNA copy number in peripheral blood
- Immunogenicity
- AE evaluation
- Concomitant medication
- Tumor imaging evaluation
- Bone marrow biopsy: repeat the bone marrow biopsy if the imaging shows CR
- Tumor biopsy: perform a tumor biopsy if clinically indicated
- Disease-related symptom evaluation
- Investigational drug administration
- Blood sampling for biomarkers
- EQ-5D-5L and EORTC QLQ-C30

Refer to Table 1 for schedule of visits during treatment.

Refer to Sections 6.3, 6.4, and 6.5 for details regarding tumor evaluation, safety evaluation, blood sampling for immunogenicity.

6.2.4 End-of-treatment visit

If the treatment ends or the investigational drug is discontinued prematurely for any reasons, an end-of-treatment visit shall be carried out as soon as possible after the investigational drug is discontinued and before the subject receives new anti-tumor therapy. The visit shall include the followings:

- Recording the vital signs and weight
- Physical examination
- ECOG PS score
- 12-lead ECG
- Count of whole blood cells/blood biochemistry/routine urinalysis
- EBV DNA copy number in peripheral blood
- Thyroid function
- Pregnancy test
- AE evaluation
- Concomitant medication
- PET-CT (if applicable)
- EQ-5D-5L and EORTC QLQ-C30

6.2.5 Safety follow-up

The safety follow-up should be performed on 90 ± 7 days after the last dose or before initiation of a new anti-tumor therapy (whichever comes first). Subjects with drug-related AEs that result in treatment discontinuation will be followed up until the AE resolves to grade 0 or 1, symptoms are stable, subject withdraws ICF, or a new anti-tumor therapy is started (whichever comes first).

- Vital signs
- Count of whole blood cells/blood biochemistry/routine urinalysis
- Thyroid function
- AE evaluation
- Immunogenicity
- Concomitant medication

6.2.6 Survival Follow-Up

After completing the safety follow-up, the subject shall be contacted with (telephone visits is allowed) once 60 days (± 7 days) to obtain the survival information, any subsequent systemic anti-tumor therapy, and PD information (for subjects with no imaging PD). Long-term follow-up shall be continued until death or end of study.

6.3 Imaging Evaluation

Baseline evaluation is conducted within 28 days prior to the first dose of the study treatment. The investigator can evaluate the imaging results within 28 days prior to the enrollment.

PET-CT and contrast-enhanced CT will be used (MRI will be performed for subjects allergic to CT contrast media). PET-CT shall be performed at baseline, week 6 (± 7 days), week 15 (± 7 days), and week 24 (± 7 days). PET-CT evaluation shall be performed at the end of treatment for subjects who discontinue the treatment prematurely prior to week 24 (unless the previous PET-CT scan is done within the past month). Contrast-enhanced CT shall be performed at baseline, week 24 (± 7 days), every 12 weeks (± 14 days) after 24 weeks, and every 24 weeks (± 14 days) after 48 weeks initiation of new anti-tumor therapy, PD, withdrawal of ICF, or death. Unplanned PET-CT and contrast-enhanced CT shall be added to evaluate the efficacy when investigators deem appropriate, if the subjects agree. The examinations will be taken at sponsor's expense. First PD shall be confirmed after 4–6 weeks. For subject who discontinue the treatment for reasons other

than PD, tumor imaging evaluation shall be continued according to the study protocol until initiation of new anti-tumor therapy, PD, withdrawal of ICF, or death.

Imaging data shall be copied or saved according to the requirements of the sponsor.

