4.1 Inclusion Criteria

1. Histologically confirmed ENKL-NT.
2. Relapsed or refractory ENKTL-NT. Being relapsed is defined as presence of new lesions at the primary location or other sites after achieving CR; being refractory is defined as any one of the followings: PD after 2 treatment cycles, PR not achieved after 4 treatment cycles, or

CR not achieved after 6 treatment cycles. Patients who do not response or patients with relapsed disease or PD after autologous stem cell transplantation can enroll.

3. Must have been treated with asparaginase-based regimen (radiotherapy must be performed for stage I/II disease).
4. Long axis of a lesion > 15 mm or ¹⁸FDG-PET uptake by lesion.
5. Eastern Cooperative Oncology Group Performance Status (ECOG PS) scores of 0–2.
6. Signed the ICFs and able to comply with the scheduled follow-up visits and related procedures required in the protocol.
7. Between the ages of ≥ 18 to ≤ 70 years.
8. Life expectancy ≥ 12 weeks.
9. Patients (female patients at childbearing age or male patients whose partners are at childbearing age) must take effective contraceptive measures during the entire course of the trial and within 90 days since the last dose of treatment (see Section 4.3).
10. Adequate organs and bone marrow functions, as defined below:
 - Count of whole blood cells: absolute neutrophil count (ANC) $\geq 1.0 \times 10^9/L$, platelets (PLTs) count $\geq 50 \times 10^9/L$, hemoglobin (HGB) ≥ 8.0 g/L; granulocyte colony-stimulating factor, PLT, or red blood cell (RBC) transfusion has not been performed within 7 days prior to the test.
 - Hepatic function: total bilirubin (TBIL) $\leq 1.5 \times$ upper limit of normal (ULN), alanine aminotransferase (ALT) and aspartate aminotransferase (AST) $\leq 2.5 \times$ ULN.
 - Renal function: serum creatinine (Cr) $\leq 1.5 \times$ ULN.
 - Thyroid function: normal thyroid stimulating hormone (TSH) at baseline, or abnormal TSH at baseline with normal T3/T4 and no symptoms.

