4.2 Exclusion Criteria

1. Patients with aggressive NK cell leukemia.
2. Patients with primary or secondary central nervous system (CNS) lymphoma.
3. Patients with severe hemophagocytic syndrome at initial diagnosis of ENKTL-NT.
4. Patients with pulmonary great vessel invasion.
5. Previous exposure to any anti-PD-1, anti-PD-L1, or anti-CTLA-4 antibodies.

6. Enrolled in another interventional clinical study, unless only involved in an observational study (non-interventional) or in the follow-up phase of an interventional study.
7. Received any investigational drug within 4 weeks prior to the first dose of study treatment.
8. The last dose of radiation or anti-tumor therapy (chemotherapy, targeted therapy, or tumor embolization) was within 3 weeks prior to receiving the first dose of study treatment; the last dose of nitrosourea or mitomycin C treatment was within 6 weeks prior to receiving the first dose of study treatment.
9. Received immunosuppressants within 4 weeks prior to the first dose of study treatment, excluding local glucocorticoids administered by nasal, inhaled, or other topical routes, or systemic glucocorticoids of physiological doses (no more than 10 mg/day of prednisone or equivalents).
10. Received any live attenuated vaccine within 4 weeks prior to the first dose of study treatment, or is scheduled to receive live attenuated vaccine during the study period.
11. Received major surgery (craniotomy, thoracotomy, or laparotomy) within 4 weeks prior to the first dose of study treatment, or has unhealed wounds, ulcers, or fractures.
12. Active, known, or suspected autoimmune disease (see Appendix 6) or previous medical history of these diseases within 2 years (patients with vitiligo, psoriasis, alopecia, or Graves' disease not requiring systemic treatment, hypothyroidism only requiring thyroid replacement, or type I diabetes only requiring insulin can enroll).
13. Known history of primary immunodeficiency diseases.
14. Known active pulmonary tuberculosis.
15. Known history of allogeneic organ transplantation or allogeneic hematopoietic stem cell transplantation.
16. Known to be allergic to any ingredients of monoclonal antibodies.
17. Uncontrolled concurrent diseases including but not limited to:
 - HIV-infected patients (positive anti-HIV antibody).
 - Active or poorly controlled severe infections.
 - Symptomatic congestive heart failure (NYHA Class III-IV) or symptomatic or poorly controlled arrhythmia.

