## STATISTICAL ANALYSIS PLAN

Innovent Biologics (Suzhou) Ltd  
Protocol number: CIBI308D201

Version: 2.0  
Version Date: 2020-02-28

---

- if month and date are missing, it will be assumed as July 1st with no conflict with other date variables;
- if dates are missing, it will be assumed as 15th with no conflict with other date variables;
- Original date collected from CRF will be shown in the listings.
- Missing data handling of other variables

Efficacy variables: All missing in the primary efficacy endpoints due to early withdrawal or lost follow up will be treated as "unable to evaluate ". In the calculation of time to event variables (e.g. PFS, DOR), subjects who have tumor evaluation missing after treatment will be reviewed to determine the time of censoring during data review meeting prior to database lock.

There will be no missing value imputation for baseline and safety data.

The extreme value of laboratory data identified as being caused by improper handling of specimens and blood samples will be replaced by unplanned visit data in the visit window (if available) as defined by the protocol. If these values cannot be replaced, they will be set as missing and be excluded from the analyses.

- Definition of baseline

The last non-missing data before first study drug administration will be defined as the baseline.

- Data derivation rules

Age (year) = (Informed Consent Date of Signature – Birth Date +1)/365.25, round to 1 decimal digits;

Course of first diagnosis (Day) = Informed Consent Date of Signature – Birth Date +1;

For efficacy related data derivation, see the sections which define efficacy endpoints.

- **Missing Relationship of AE to Study Treatment**

If relationship is missing, no imputation is made but will be considered as related.

- **Missing CTCAE grade**

Missing grade will not be imputed but will be counted in summary as grade  $\geq 3$  and will be listed separately.

- **Handling of Outliners**

NA

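### The 28-day baseline scan window is longer than the 21-day washout and the scan need not follow the last prior treatment, so prior-therapy shrinkage can enter the primary ORR

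*Protocol*

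**What the plan says.** **Scan window.** Protocol 6.3 opens with "Baseline evaluation is conducted within 28 days prior to the first dose of the study treatment". Its next sentence counts from another date: "The investigator can evaluate the imaging results within 28 days prior to the enrollment". Protocol 6.2.1 lists tumour imaging among the screening procedures and says "The following procedures must be completed during the screening (Day -28 to -1) to ensure subject eligibility". Table 1 uses the same window.

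**Washout.** Exclusion 8 in Protocol 4.2 covers subjects for whom "The last dose of radiation or anti-tumor therapy (chemotherapy, targeted therapy, or tumor embolization) was within 3 weeks prior to receiving the first dose". A longer period applies where "the last dose of nitrosourea or mitomycin C treatment was within 6 weeks prior to receiving the first dose of study treatment". Exclusion 7 sets 4 weeks for investigational drugs.

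**Eligibility.** Inclusion 2 in Protocol 4.1 accepts as refractory a subject with "CR not achieved after 6 treatment cycles".

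**Analysis baseline.** SAP 4.3 states "The last non-missing data before first study drug administration will be defined as the baseline". SAP 4.2, on special handling of efficacy data, is marked not applicable. SAP 5.5.1 counts any CR or PR as best overall response and gives ORR an exact binomial 95% interval.

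**The concern.** In a single-arm trial, ORR can be read as a drug effect only if the baseline scan shows the disease with which IBI308 treatment starts. If the scan predates the last dose of earlier chemotherapy or radiotherapy, shrinkage caused by that therapy lies between baseline and the week-6 PET-CT and can be recorded as a response to IBI308. There is no control arm in which the same artefact would appear. ORR, CR and DCR would be overstated, and TTR would include responses that began before treatment. The refractory definition makes this plausible, because a subject in partial response to the previous regimen can enter.

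**Working it through.** **1. Date arithmetic (all relative to first dose).**

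| Prior therapy | Washout | Scan window | Overlap |
|---|---|---|---|
| Radiotherapy, chemotherapy, targeted therapy, embolization | 21 days | 28 days | 28 - 21 = 7 days |
| Investigational drugs | 28 days | 28 days | none |
| Nitrosourea, mitomycin C | 42 days | 28 days | none |

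The overlap covers Day -28 to Day -22. For example, a scan on Day -28 and a chemotherapy dose on Day -22 satisfy both the imaging window and exclusion 8. If the 28 days were counted from enrolment, and enrolment came k days before first dose, the overlap would be 7 + k days. The documents give no value or maximum for k.

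**2. Search for an ordering rule.** None is stated in Protocol 6.3, Table 1 notes 15 and 16, Protocol 6.2.1, inclusion 4, or SAP 3.1, 4.2 and 4.3. The SAP rule of taking the last value before first dose helps only if a second, later scan exists.

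**3. The plan's own figures.**
- Sample size, normal approximation: n = [(1.960 × √(0.30 × 0.70) + 0.842 × √(0.50 × 0.50)) / 0.20]² = 43.49, against the stated 43. Power at n=43 is 79.6%.
- The amendment summary reports 67.9% ORR in 28 subjects: 0.679 × 28 = 19 responders.

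**4. Success rule.** An exact 95% lower limit above 30% needs 14/28 (lower limit 30.6%) or 20/43 (31.2%). At a true ORR of 30% the chance of reaching it is 2.1% and 1.6% respectively.

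**5. Illustration. The inputs f and r are assumptions, not taken from the documents.** Let f be the share of subjects scanned before their last prior dose. Let r be the chance that a true non-responder among them reads as CR or PR through carry-over. Then

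apparent ORR = 0.30 + f × r × 0.70.

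- f = 10%, r = 20%: 0.30 + 0.10 × 0.20 × 0.70 = 31.4%
- f = 30%, r = 40%: 0.30 + 0.30 × 0.40 × 0.70 = 38.4%

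| | No carry-over (30%) | 31.4% | 38.4% |
|---|---|---|---|
| False success, n=43 | 1.6% | 2.7% | 17.4% |
| False success, n=28 | 2.1% | 3.1% | 14.3% |

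Each wrongly credited responder adds 1/28 = 3.6 points, or 1/43 = 2.3 points.

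**6. Against the reported result.** The exact lower limit for 19/28 is 47.6%. Removing five responders leaves 14/28, with a lower limit of 30.6%. Removing six leaves 13/28, with a lower limit of 27.5%. So six of the 19 would have to be carry-over before the limit fell below 30%.

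**The case against.** **The enrolment sentence is not the source of the gap.** A reader might infer from it that much older scans are acceptable. The documents do not support that: the preceding sentence of 6.3, section 6.2.1 and Table 1 all point to Day -28 as the limit, and the sentence can be read as allowing existing scans within that limit. This stands. The 7 days come from the first-dose window and exclusion 8; the enrolment sentence is a conflict to reconcile.

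**Other safeguards narrow the route.** Consent must precede any protocol procedure (Protocol 6.1.1, Table 1 note 1). Other anti-tumour therapy, palliative radiotherapy excepted, is prohibited in 5.5.1 with no start date given. The sponsor's medical manager reviews each subject's eligibility information before enrolment. A protocol scan followed by chemotherapy would therefore be questionable. This stands in part: the most plausible route is a reused scan from before consent, and none of these safeguards orders scan and therapy.

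**The bias need not run upward.** A reader might infer that an early baseline can only inflate ORR. It can also miss growth before the first dose, which would lower ORR, and the amendment summary reports several early progressions. This stands. The false-success figures describe the carry-over direction only.

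**Partial response at entry is a separate matter.** A reader might infer that subjects entering in partial response are still shrinking. The inclusion criterion does not say so. Such a subject could also go on shrinking after a scan correctly taken after the last dose, so an ordering rule would not remove that effect.

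**The change comes late.** The amendment summary says enrolment was paused at 28 and sees no need to reach 60. New wording in 6.3 cannot alter scans already taken. This stands for the protocol text but not for the SAP analysis.

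**Conclusion.** The point holds as a gap in the rules: the text permits up to 7 days in which the response baseline can predate the last prior radiotherapy, chemotherapy, targeted therapy or embolization. It does not arise for nitrosourea, mitomycin C or investigational drugs under the first-dose anchor. The date arithmetic is certain. The size of any bias is unknown, because the documents do not show how many subjects, if any, were scanned in that interval. The 2.7-17.4% (n=43) and 3.1-14.3% (n=28) figures depend wholly on the assumed f and r, and their upper ends need both at the maximum.

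A reader might infer that the trial's positive conclusion is in doubt. The reported figures do not support that, since six of 19 responders would have to be artefacts. That margin rests on the 67.9% in the amendment summary, which takes pseudo-progression into account. The estimates of ORR, CR, DCR and TTR are more exposed than the conclusion. This is an inexpensive improvement worth making, and the SAP part is what can still have an effect.

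**What to change.** **Protocol 6.3.** Use one anchor, within 28 days before first dose, and remove or reword the enrolment sentence to agree with it and with 6.2.1. State that the PET-CT and CT used as the response baseline must be taken after the last dose of prior anti-tumour therapy. The washout in exclusion 8 is not changed.

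**SAP.** List, for every subject, the interval from last prior anti-tumour therapy to baseline scan. Add an ORR sensitivity analysis in which responders whose baseline scan predates the end of prior therapy count as non-responders. Label it a worst case, because some of them may be true responders. If no subject is affected, the listing alone settles the question.

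**Cost.** The change takes a short edit to 6.3, one listing and one sensitivity row. The last-therapy and scan dates should already exist, since they are needed to check eligibility. There are no new visits or procedures, and the sample size of 43 is unaffected. The downside is that an occasional routine-care scan could not be reused, and the sensitivity ORR may be slightly lower than the primary one.

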6.4 Safety Evaluation

6.4.1 Routine laboratory safety evaluations

Table 4. Routine laboratory safety evaluations

Count of Whole Blood Cells	RBC, HGB, WBC, PLT, LYM, and ANC
Blood Biochemistry	TBIL, ALT, AST, γ -GT, ALP, ALB, TP, LDH, BUN, Cr, Na, K, Cl, Mg, Ca, P, lipase, amylase, and FBG
Routine Urinalysis	PH, UALB, UPRO, URBC, and UGLU

6.4.2 Physical examination

A comprehensive physical exam includes general conditions, respiratory tract, cardiovascular system, abdomen, skin, head and neck (including ears, eyes, nose, and throat), lymph nodes, thyroid, musculoskeletal system (including spine and limbs), genitalia/anus, and nervous system.

Refer to the schedule of visits in Table 1 for examination time. Refer to Appendix 2 for ECOG PS criteria.

6.4.3 12-lead ECG

A resting 12-lead ECG is performed at the local laboratory in accordance with the schedule of visits in Table 1.

A 12-lead ECG examination will be performed after the subject rested for at least 5 minutes in the supine position. All 12-lead ECGs should be recorded while the subject is resting in a supine position. Further ECG shall be performed if clinically indicated, such as a cardiac AE. The investigator shall review the ECG on the day it is performed, and document the results on the ECG. The same method of evaluation shall be used throughout the trial.

The investigator shall evaluate all the ECG as either a clinically significant/insignificant abnormality. If it is a clinically significant abnormality, the investigator shall document the results as an AE in the eCRF.

